9.2 Screening and Eligibility Assessment

All information required to screen participants will already be known to clinical members of the research team as part of their role in the participant's routine care. On the basis of this information, clinical members of the research team will approach prospective participants and invite them to participate. If the participant accepts the invitation, they will be screened for exclusion criteria.

9.3 Informed Consent

Written and verbal versions of the appropriate participant information and informed consent forms will be presented to the participants detailing no less than: the exact nature of the study; what it will involve for the participant; the implications and constraints of the protocol; and any risks involved in taking part. It will be clearly stated that the participant is free to withdraw from the study at any time for any reason without prejudice to future care, and with no obligation to give the reason for withdrawal.

The participant will be allowed to consider the information, and the opportunity to question the investigator, their GP or other independent parties to decide whether they will participate in the study, although this is limited by the fact that participants will need to decide whether or not to take part in the study on the day they are approached. For Streams 1 and 2, written informed consent will then be obtained by means of participant dated signature and dated signature of the person who presented and obtained the informed consent. The person who obtained the consent must be suitably qualified and experienced, and have been authorised to do so by the Chief/Principal Investigator. A copy of the signed informed consent form will be given to the participant. The original signed form will be retained at the study site and filed in the site file – this will be kept securely locked in a locked office. A copy of the consent form will be kept in the patient's medical record.

For stream 3 (the qualitative interviews), remote consent will be obtained by a member of the local research team via Microsoft Teams or telephone. Consent forms will be completed by a suitably qualified and experienced member of the local research team on behalf of the participant. The participant will be emailed a copy of their consent form. Consent forms will be retained at the study site – this will be kept securely locked in a locked office. Once consent has been obtained the name and email address of the participant will be passed on to the central study team for the purpose of arranging the interview.

9.4 Enrolment

This study does not involve randomisation. At the point of recruitment, a member of the research team will assist the participant in downloading the EMCAT app and enabling push notifications.

9.5 Blinding and code-breaking

There will be no blinding in this study.

9.6 Description of study intervention(s), comparators and study procedures (clinical)

This is an observational and not an interventional study.

9.6.1 Description of study procedure(s)

EMCAT is a progressive web application maintained by the University of Cambridge Psychometrics Centre. Each day for the first 12 weeks, it will prompt participants to complete an assessment, either by email and/or push notification. Participants undergoing steroid injection for TBOA will receive twiceweekly notifications for a further 12 weeks. When a participant receives a notification, they can choose to engage with the EMCAT app, or dismiss the notification. Those who choose to engage will either click on a hyperlink in an email, or on a push notification button to start the assessment. The application will pose questions from the PEM questionnaire which the participant will be able to respond to by clicking response options (See Appendix A).

After each response, the application will automatically select the next most useful question to administer. This process is continued until a prespecified stopping rule is met (standard error of measurement < 0.3). We expect that participants will be asked to complete between 1 and 4 questions each time they are notified. EMCAT responses will be collected for a period of 12 weeks (24 weeks for those undergoing steroid injection for TBOA). We may vary the time of day these notifications are scheduled for throughout the study, to reduce server demands.

In addition to the PEM EMCAT, each participant will be asked to complete the full-length PEM part 2 questionnaire (11 questions) at 0, 6 and 12 weeks via the app. At 12 weeks, we will ask participants to complete the User Engagement Scale (UES, 31 questions), also via the app. It is possible that participants who have had a negative experience of the app do not return UES data through it. Therefore, participants who do not respond to the UES via the app will be contacted via email and/or telephone and offered the opportunity to complete the UES either through the app reminder, over email or over the telephone. The method of response to the UES will be recorded, if not through the EMCAT platform.

9.7 Study visit

At the point of recruitment, a member of the research team will assist the participant in downloading the EMCAT app and enabling push notifications. A spreadsheet will be updated with the participants study number, eligibility status, reason for exclusion if applicable, age, sex, ethnicity, employment status, hand dominance, as well as the treatment they are undergoing, the date and the timing of the EMCAT scheduling.

The participant will complete a single full-length PEM assessment and an EMCAT PEM assessment via the application at this appointment.

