6. OBJECTIVES AND OUTCOME MEASURES

Objectives	Outcome Measures	Timepoint(s) of evaluation of this outcome measure (if applicable)
Primary Objective		
1. Compare the recovery trajectories of patients undergoing percutaneous needle fasciectomy (PNF) to patients undergoing limited fasciectomy (LF), to test whether EMCAT can detect different recovery trajectories over a 12-week period, with less severe post-treatment symptoms in the PNF group within the first 4 weeks.	The PEM, administered via EMCAT.	Trajectories will be plotted and compared over a 12-week period.
Secondary Objectives		
2. Compare the recovery trajectories of other groups that are expected to differ over a 12-week period. Specifically, we will test the following hypotheses, which are based on the researchers' clinical experience:	The PEM, administered via EMCAT.	Trajectories will be plotted and compared over a 12-week period.
 Steroid injection results in less severe post-treatment symptoms than trapeziectomy, within the first 4 weeks 		
 Trapeziometacarpal arthroplasty results in less severe post- treatment symptoms than trapeziectomy, within the first 4 weeks 		
 Minimally invasive (endoscopic or percutaneous) CTD results in less severe post-treatment symptoms than open CTD, within the first 2 weeks 		
 The difference in the recovery of groups undergoing open release vs steroid injection for trigger finger are not clinically significant over the first 2 weeks 		
The objective is to test EMCAT's ability to differentiate between recovery trajectories that are expected to differ, rather than to prove or disprove that differences in recovery trajectory exist. The clinical comparisons are a vehicle for testing the measurement properties of EMCAT. Here, the threshold for clinically significant difference is approximated as half a standard deviation of baseline scores of groups being compared. Statistical significance is taken at the 5% level. By symptom severity, we mean PEM EMCAT scores, where a higher (poorer) score reflects more severe symptoms (a poorer level of hand health).		

	UES scores,	12-week follow-up
3. Assess the usability of the EMCAT platform	response rates, response times, and semi- structured interviews	
4. Assess the criterion validity of EMCAT against the full-length PEM by comparing scores at baseline, 6 weeks, and 12 weeks	Full-length PEM scores and EMCAT PEM scores	Baseline, 6-week and 12-week follow-up
Exploratory Objectives		

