9.12 Study sequence

- 1. Potential participants will be identified by clinical members of the research team during routine care.
- 2. The clinical team members will invite potential participants to participate on the day of their treatment.
- 3. Potential participants will be provided with a written information pack, and given time to read this and discuss it.
- 4. The investigator will take informed consent from the participant at that point, if the participant feels they have had sufficient time to consider taking part.

- 5. At the point of recruitment, a member of the research team will assist the participant in downloading the EMCAT app and enabling push notifications.
- 6. At the point of recruitment, prior to the treatment, the participant will complete the full-length (11-item) PEM part 2 via the EMCAT app, and a single EMCAT assessment.
- 7. Over the next 12 weeks, participants will complete daily PEM EMCAT questionnaires (if they choose to) when prompted by email or push notification.
- 8. In addition, at 6 and 12 weeks, participants will be asked to complete the full-length PEM part 2 via the app, separately.
- 9. At 12 weeks, participants will also be asked to complete the UES via the app. Participants who do not respond with 7 days will be contacted via email or telephone and asked if they would like to return UES responses either via email or over the telephone. The method of UES response (app/email/telephone) will be recorded, if not via the ECMAT platform.
- 10. At 12 weeks, notifications will stop for all participants except those who underwent steroid injection for TBOA these participants will continue to receive EMCAT notifications twice weekly for a further 12 weeks.
- 11. For participants undergoing steroid injection for TBOA or open CTD, at the 24-week timepoint, a clinical member of the research team will review the participant's medical record and record follow-up appointment dates and (for those who underwent open CTD) whether the follow up resulted in a change of management.
- 12. Three independent clinicians will review de-identified EMCAT trajectories and appointment dates for patients who underwent open CTD, and predict whether each participant required a change in management.
- 13. We will identify and approach 10 patients and 10 clinicians with invitations to take part in semistructured interviews – interviews will take place no later than 14 days after finishing use of the EMCAT platform.

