11.4 Description of the Statistical Methods

The hypotheses outlined in the primary and secondary objectives will be tested with mixed-effects linear modelling. These models will comprise: EMCAT score (continuous dependent variable on a logit scale, derived from a graded response model); participant number (random intercept); age, sex, and baseline score (fixed effects); and an interaction term between time (number of days following the intervention) and treatment allocation. Marginal means will be derived from these models and between-group differences calculated at daily timepoints after Tukey adjustment for multiplicity. This will be performed with the *emmeans* R package, or equivalent software. For each comparison, marginal means will be plotted, and differences compared to a minimal important difference (MID) estimate of half a standard deviation of baseline scores. Clinically and statistically significant (at the 5% level) differences will be compared to those predicted (see section 6).

EMCAT completion rates (number of completed response sets divided by number of invitations), response times, and UES scores will be analysed through descriptive statistics. The UES was originally intended to measure 6 user engagement constructs, but subsequent studies have suggested that it follows a 4-factor structure. Items of the UES will be grouped into the 4 subscales described by O'Brein et al, to measure: focused attention, aesthetic appeal, perceived usability and reward⁵.

The criterion validity of the EMCAT scores against the full-length PEM scores will be assessed by comparing pairs of EMCAT scores and full-length PEM scores that were obtained from the same participant on the same day. Comparison will be made by calculating Pearson's correlation coefficient, mean absolute error, root mean squared error and the Bland-Altman method⁶.

In Stream 2, three independent clinicians will review EMCAT trajectories (presented as time series plots) and follow-up appointment dates for participants that underwent open CTD. They will be asked to predict whether a change in management was required at the follow-up appointment. We will calculate inter-rater reliability of these assessments (Fleiss' kappa) and, for each clinician, the accuracy, sensitivity, specificity, positive predictive value and negative predictive value of their predictions against the reference standard (whether or not the patient received a change in management).

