12.5 Data Recording and Record Keeping

Informed consent forms will be kept in the site file, which will be securely stored in a locked office, or electronically, at the recruitment site, in line with local policy. These will be stored for 3 years following the study end date. A copy of the informed consent form will be kept in the participant's medical notes for as long as those notes are retained.

Participants will be identified by a unique study specific number and/or code. For each participant, pseudonymised study data (study number, eligibility status, reason for exclusion if applicable, age, sex, ethnicity, employment status, hand dominance, as well as the treatment they are undergoing, the date and the timing of the EMCAT scheduling) will be directly entered onto a password-protected Excel spreadsheet, which will be stored securely at each site, in line with local policy.

For participants recruited at a given site, study numbers will be linked to participants names, hospital numbers and email addresses with a password-protected excel spreadsheet, securely stored at the site, with access limited to research team members at that site. This is a different spreadsheet to the one that will collect pseudonymised study data. This will allow the research team to identify study participants when required for the purpose of the study, and allow clinical members of the team to access patient records to record data collected in Stream 2. It is necessary to include the email addresses in this document as they will be used to inform participants once the results of the study have appeared in the public domain, enable the research team to contact participants to troubleshoot with any issues that arise with the EMCAT application, and allow the research team to recruit participants to the qualitative research stream. As soon as participants have been notified that the results of the study are in the public

domain, these spreadsheets including the email addresses will be deleted. This information will only be stored locally, and not transferred to the central research team.

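### Beyond baseline PEM, age and sex, the planned dataset says nothing about the Dupuytren's disease, so the non-randomised PNF versus LF contrast cannot be adjusted for disease extent or recurrence

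*Protocol*

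**What the plan says.** Section 9.4 of the protocol states: "This study does not involve randomisation". Treatment is whatever the participant is already due to receive.

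Section 9.7 lists what the site spreadsheet holds: study number, eligibility status, any reason for exclusion, then "age, sex, ethnicity, employment status, hand dominance, as well as the treatment they are undergoing", with the date and the EMCAT scheduling. Section 12.5 gives the same list for data management.

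The next paragraph of 9.7 adds a severity measure: "The participant will complete a single full-length PEM assessment and an EMCAT PEM assessment via the application at this appointment". Section 9.12 confirms that this comes before treatment. The covariates of the primary model in 11.4 are "age, sex, and baseline score (fixed effects", alongside a time-by-treatment interaction and a random intercept.

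Sections 6 and 7 predict less severe symptoms after PNF than after LF within the first 4 weeks. They add that the clinical comparisons serve to test EMCAT and are not meant to settle whether recovery really differs.

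**The concern.** When treatment is chosen clinically, the groups may differ in how much disease they have and whether it has been treated before. Both could plausibly affect the choice of procedure and the first weeks of recovery. Baseline PEM captures how the hand is before treatment. It does not say how many digits or joints are affected, or whether the disease is recurrent. Two participants with equal baseline scores can differ on all of these.

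At stake is how the primary result can be read. Section 11.4 compares the observed differences with the predicted ones. If LF participants have more extensive disease, part of a difference in the predicted direction is case mix and not the expected procedural difference. If the mix runs the other way, a procedural difference could be masked, and the null result might wrongly be held against EMCAT. Adding every other recorded covariate (ethnicity, employment status, hand dominance) would not help, because none of them describes the disease. The public dataset would carry the same gap.

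**Working it through.** **1. The plan's own figure (11.5).** Inputs: effect 0.35, SD 1, 90% power, 5% significance, taken as two-sided.

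- n per group = 2 × (1.960 + 1.282)² / 0.35² = 171.5, so 172 per group and 344 in total. This reproduces.
- 172 × 1.15 = 198 and 344 × 1.15 = 396. These reproduce as stated. Dividing by 0.85 would give 203 and 405, but the present point does not depend on that.

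**2. What is recorded for PNF and LF participants.**

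| Kind of variable | Recorded? | Where |
|---|---|---|
| Age, sex | Yes, in the model | 9.7, 11.4 |
| Pre-treatment PEM (full-length and EMCAT) | Yes; baseline score in the model | 9.7, 9.12, 11.4 |
| Ethnicity, employment, hand dominance | Yes, not in the model | 9.7, 12.5 |
| Treatment name, date, scheduling | Yes | 9.7, 12.5 |
| Digits or joints affected | No | – |
| First-time or recurrent disease | No | – |

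**3. Other routes to the missing data.**

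- Record review at 24 weeks (9.12, 12.5) covers only steroid injection for TBOA and open CTD.
- Section 12.3 names hospital records as a source, but only generically, for medical history and medication.
- Sections 11.3 and 12 say there is no separate SAP or data management document.
- Section 11.10 plans no sensitivity analyses.
- Section 12.5 keeps a site-held link from study number to hospital number until participants have been told of the results. Retrieval is therefore possible in principle, but it is not planned.

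**4. Illustrative size.** The documents give neither input, so these values are assumed. Suppose 20% of one group and 50% of the other have extensive or recurrent disease, and that this worsens the early score by 0.2 to 0.5 SD given baseline PEM, age and sex.

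- Bias = difference in prevalence × effect = (0.50 − 0.20) × 0.2 to 0.5 = 0.06 to 0.15 SD.
- Relative to the design effect: 0.06 / 0.35 = 17%; 0.15 / 0.35 = 43%.
- The sign depends on which group has more extensive disease.

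**5. What that does to a test.** Use a simple two-group comparison with 172 per group, SE = √(2/172) = 0.108. This approximates the planned mixed model.

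- No true difference, bias 0.06: 0.06 / 0.108 = 0.56, so P(significant) is about 9% instead of 5%.
- No true difference, bias 0.15: 0.15 / 0.108 = 1.39, so P(significant) is about 28%.
- True difference 0.35, bias −0.15: the net difference is 0.20, and 0.20 / 0.108 = 1.85, so power is about 46% instead of 90%.

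**6. How far the assumptions matter.** Treat extent as a continuous measure, with imbalance of 0.25 to 1.0 SD and residual effect of 0.1 to 0.5 SD. The bias then runs from 0.25 × 0.1 = 0.025 to 1.0 × 0.5 = 0.50 SD, or 7% to 143% of 0.35. The figures show that the bias could matter; they do not estimate it.

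**The case against.** The strongest reply is that this is not meant as a causal comparison. Sections 6 and 7 say so. If LF participants recover more slowly partly because their disease is more extensive, their trajectories do differ, and EMCAT is right to show it. This stands: a difference due to case mix is still a difference between the groups. What remains is that the prediction is framed around the procedures, so without disease data nobody can say which difference EMCAT detected, or why it found none.

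A reader might infer that case mix is not adjusted for at all. That is wrong: baseline PEM is taken before treatment and is in the model, so case mix that shows in current hand symptoms is partly handled.

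A reader might also infer that no later analysis could ever repair the gap. The documents do not support that either, because the site-held link would allow retrieval while it exists, if approvals and consent covered it. The limit applies to the planned dataset.

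Section 8.3 excludes bilateral treatment and planned multiple treatments to the affected hand. This may narrow the spread of disease extent. It does not deal with recurrence or joints affected, and it is unclear whether it covers several digits treated in one session.

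Finally, no section says that extent or recurrence drives the choice of procedure or early PEM scores. That premise is plausible, but it is an assumption.

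**Conclusion.** The point holds as a limit on interpretation. The planned dataset has no variable describing the Dupuytren's disease, so confounding by extent or recurrence left after adjustment for baseline PEM, age and sex can be neither examined nor adjusted for. A result in the predicted direction may partly reflect case mix. A null or reversed result could not be attributed to EMCAT or to case mix.

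The size is unknown. Under the assumed 30-point prevalence gap and 0.2 to 0.5 SD effect, it is 0.06 to 0.15 SD in either direction. It would be zero if the groups were balanced on extent and recurrence, or if these had no effect beyond baseline.

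It would go too far to conclude that the primary objective is invalid or that the contrast is known to be biased. The stated aim is to test a measurement tool, and no figure in the protocol establishes an imbalance. This is an inexpensive improvement worth making.

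**What to change.** In 9.7 and 12.5, add fields to the site spreadsheet for Dupuytren's participants, recorded before treatment: first-time or recurrent disease, and the digits and joints affected. Report them by group. In 11.4, specify a PNF versus LF model with these as extra fixed effects, presented alongside the planned model, and amend 11.10 so that this second analysis is allowed.

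Record digits treated for description only. It is partly a feature of the procedure, and adjusting for it could remove some of the difference that EMCAT is meant to detect.

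For participants already enrolled, fill the fields from records only if approvals and consent cover that access; 16.6 describes record access for Stream 2 only. Any backfill must be done before the linkage files are deleted. Otherwise, state the limitation in the report.

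The cost is a little more site data entry, an amendment to the data list and a few model terms. Section 9.2 says "All information required to screen participants will already be known to clinical members of the research team", but the criteria in 8.2 and 8.3 do not ask about recurrence or joints, so that sentence does not show that staff already hold these details. Sites should confirm that they can be obtained on the enrolment day.
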